Methodology	Prospective clinical trial
Study Duration	15 months
Study Center(s)	Single center
Objectives	The purpose of this study is to evaluate the incremental benefit of Fractional Flow Reserve (FFR) derived from Coronary Computed Tomographic Angiography (CCTA) (CT-FFR) compared to CCTA with or without stress testing, using invasive FFR as the gold standard for patients with obstructive disease (> 30% stenosis). This study will also assess the capability of CT-FFR to enhance performance on both negative and positive predictive value for less experienced readers by providing feedback based on CT-FFR evaluation
Number of Subjects	Number of subjects projected for the entire study 572
Diagnosis and Main Inclusion Criteria	Chest Pain and stable angina patients with suspicion of coronary artery disease
Study Product, Dose, Route, Regimen	n/a. The study will assess the capability of measuring fractional flow reserve noninvasively utilizing computers and information provided by routine CCTA studies.
Duration of administration	n/a
Reference therapy	The standard reference will be invasive FFR.
Statistical Methodology	Defining an event as performance of ICA when no intervention is necessary, we expect to compare event rates for patients treated with CCTA and FFR-CT, using t-tests and a multivariate, risk adjusted 90 day hazard model with 95% confidence interval. Our null hypothesis is that outcomes will not vary regardless of which testing is used to assess obstructive disease. Our alternative hypothesis is that evaluation with FFR-CT as oppose to CCTA alone will reduce the event rate. We will assess the comparability of the CCTA readers' readings and compare them to the CT-FFR results and the noninvasive FFR results.

1 Previous Study History

Has this study ever been reviewed and rejected/disapproved by another IRB prior to submission to this IRB?

No Yes – if yes, please explain:

2 Brief Summary of Research

Coronary Computed Tomography Angiogram (CCTA) is a non-invasive imaging modality that has high sensitivity and negative predictive value for the detection of coronary artery disease (CAD). The main limitations of CCTA are its poor specificity and positive predictive value, as well as its inherent lack of physiologically relevant data on hemodynamic significance of coronary stenosis, a data that is provided either by non-invasive stress tests such as myocardial perfusion imaging (MPI) or invasively by measurement of the Fractional Flow Reserve (FFR). Recent advances in computational fluid dynamic techniques applied to standard CCTA are now emerging as powerful tools for virtual measurement of FFR from CCTA imaging (CT-FFR). These techniques correlate well with invasively measured FFR [1-4]. The primary purpose of this study is to evaluate the incremental benefit CT-FFR as compared to CCTA in triaging chest pain patients in outpatient settings who are found to have obstructive CAD upon CCTA (> 30% stenosis). Invasive FFR and short term clinical outcomes (90 days) will be correlated with each diagnostic modality in order to evaluate positive and negative predictive value of each when used incrementally with CCTA.

Patients will undergo a CCTA, as part of routine care. If the patient consents to participate in the study and is found to have coronary stenosis of 30% to 100%, based on the cardiologist's reading, the CCTA study will be sent to HeartFlow, a vendor that will provide a computerized FFR reading, based on the CCTA study. If the noninvasive FFR diagnosis indicates obstructive disease, the patient will undergo cardiac catheterization with invasive FFR.

As CCTA utilization increases, the need to train additional imaging specialists will increase. This study will assess the capability of FFR-CT to enhance performance on both negative and positive predictive value for less experienced readers by providing feedback based on CT-FFR evaluation. CCTA readers will be grouped in two categories: those with more than 10 years reading experience and those with less than 10 years reading experience. Each CCTA will be read by a less experienced and a more experienced reader. Results from each reader will be correlated with each other and with the CT-FFR and invasive FFR results.

3 Introduction

This document is a protocol for a human research study. This study is to be conducted according to US and international standards of Good Clinical Practice (FDA Title 21 part 312

and International Conference on Harmonization guidelines), applicable government regulations and Institutional research policies and procedures.

3.1 Background

Coronary Computed Tomography Angiogram (CCTA) is a non-invasive imaging modality that has high sensitivity and negative predictive value for the detection of coronary artery disease (CAD). The main limitations of CCTA are its poor specificity and positive predictive value, as well as its inherent lack of physiologically relevant data on hemodynamic significance of coronary stenosis, a data that is provided either by non-invasive stress tests such as myocardial perfusion imaging (MPI) or invasively by measurement of the Fractional Flow Reserve (FFR). Recent advances in computational fluid dynamic techniques applied to standard CCTA are now emerging as powerful tools for virtual measurement of FFR from CCTA imaging (FFR-CT). These techniques correlate well with invasively measured FFR [1-4]. The primary purpose of this study is to evaluate the incremental benefit FFR-CT as compared to CCTA in triaging chest pain patients in outpatient settings who are found to have obstructive CAD upon CCTA (> 30% stenosis). Invasive FFR and short term clinical outcomes (90 days) will be evaluated for each diagnostic modality in order to evaluate positive and negative predictive value of each when used incrementally with CCTA.

3.2 Investigational Agent

CCTA is increasingly becoming a preferred non-invasive imaging modality because of its high sensitivity and negative predictive value for the detection of CAD. It has been shown to be a robust imaging modality for evaluation of chest pain, and is associated with decreased unnecessary hospital admission, length of stay, major adverse cardiovascular event rates, recidivism rates, and downstream resource utilization compared to standard evaluation [5]. While findings so far are highly suggestive of CCTA's significance as a gatekeeper for ICA by ruling out obstructive CAD, fewer than half of obstructive stenosis identified by CCTA are ischemia-causing, signifying its poor positive predictive value and inherent lack of physiological information [6-8]. Consequently, utilization of CCTA has not entirely averted need for downstream testing for functional assessment of CCTA-detected obstructive lesions either by stress testing or ICA. Recently a major treatment modality, associated with the use of CCTA, has become available that offers promise for improving positive predictive value and physiological relevant hemodynamic data. Advances in computational fluid dynamic techniques applied to standard CCTA are now emerging as a powerful tool for virtual measurement of FFR from CCTA imaging (CT-FFR). This techniques correlate well with invasively measured FFR [1-4]. CT-FFR is not an investigational agent, having been approved by FDA in November, 2014. However, more work is necessary to delineate the patient population that could derive maximal benefit from this new technology.

3.3 Preclinical Data

While few publications regarding the use of CT-FFR specifically address the cost of diagnostic work-up for obstructive disease, it is clear that the cost structure resulting from changes in diagnostic testing will also change. Deferral or avoidance of cardiac catheterization and nuclear stress testing will likely yield significant reductions in the cost of the diagnostic testing.

3.4 Clinical Data to Date

From 1/1/2009 to 3/31/2015 our team introduced and operated a CCTA Chest Pain triage program for low to intermediate risk patients at Stony Brook University Hospital ED and non-emergency outpatient services, the only tertiary care hospital in Suffolk County. Concurrently, we established a registry to monitor patient outcomes for all patients receiving CCTA at Stony Brook Medicine. Our registry contained nearly 15,000 patient CCTA procedures. Our major registry study established the effectiveness of CCTA as an imaging modality for evaluating ED chest pain in a cost efficient manner with a false negative rate less than 1% [5]. However, our registry reflects the poorer positive predictive values documented by other industry studies [6-8].

False positive workup results in the necessity of performing cardiac catheterization on patients at risk for obstructive disease based on assessment with current standard of care (combined screening with CCTA and stress MPI). Reduction in the rate of false positive testing would lead to reduction in risk from invasive procedures and radiation exposure to patients and reduced cost to the health care system.

Several medical institutions currently use HeartFlow CT-FFR as standard of care for evaluating obstructive disease. Generally, the standard of care at these institutions is to refer patients who are 30 to 100 percent obstructed by CCTA and who have reduction of flow \leq to 0.8 that is deemed to be medical significant by the attending cardiologist to Invasive FFR. HeartFlow has reported to us confidentially that this routine use of CT-FFR has resulted in a 54% reduction in false positive rate as compare to use of CCTA alone.

3.5 Dose Rationale and Risk/Benefits

n/a This is not a pharmaceutical study.

4 Study Objectives

The purpose of this study is to evaluate the incremental benefit of Fractional Flow Reserve derived from CCTA (FFR-CT) compared invasive FFR as the gold standard for patients with obstructive disease ($> 30\%$ stenosis). This study will also assess the capability of CT-FFR to

enhance performance on both negative and positive predictive value for less experienced readers by providing feedback based on CT-FFR evaluation.

5 Resources Available to Conduct the Human Research

The primary data collection for the study will be generated from stable chest pain and angina patients receiving routine CCTA as part of their workup. Patients will be offered the opportunity to participate in clinical trial. Lenox Hill hospital routinely provides more than 1,000 CCTA scans annually to this patient population. Therefore, our target of 572 cases should be achievable. Our noninvasive cardiology imaging team, including 6 attending cardiologists, and 2 cardiology fellows, and a cardiac imaging fellow will participate in the study. In addition, we will employ a study coordinator, an IT specialist who works in cardiology, our lead CCTA technician, and a PhD with training in statistics and economics. All team members attend weekly research group meetings to plan and monitor the study, including duties of team members and study process and flow.

6 Study Design

[figure not shown]

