6.1 General Design

This will be a prospective clinical trial designed to evaluate the incremental benefit of virtual FFR measured from CCTA, compared to invasive FFR and CCTA for the detection of flow-limiting coronary stenosis, as defined by invasive FFR ≤ 0.8 and vessel diameter of $\geq 2\text{mm}$.

572 consecutive patients who present to Lenox Hill Hospital Outpatient Clinics for CCTA due to chest pain or stable angina over a ten month period and meeting the study inclusion criteria are eligible for the study (Figure 1). Our team will employ CCTA-appropriateness criteria to ensure proper selection of patients, derived from the Appropriate Use Criteria for Cardiac Computed Tomography published in 2010 and jointly authored by multiple societies including ACCF, SCCT, and ACR [10]. FFR-CT measurements will be performed by a core laboratory in a blinded fashion. All eligible patients will undergo 64-slice or greater multi detector CCTA and CT-FFR measurements. The severity of the stenosis will be determined on site by level III CCTA readers. Patients with obstructive lesions of (30% to 100% stenosis) will receive Stress-MPI, per SOC protocol, and CT-FFR. Patients with positive Stress-MPI and CCTA (50% - 70%) or positive CCTA (71% to 100%) will undergo ICA with invasive FFR measurement in accordance to accepted guidelines and established practice standard. Those patients with invasively measured FFR ≤ 0.8 and with vessel diameter of $\geq 2\text{mm}$, or those who require revascularizations based on invasively estimated stenosis severity will be considered to have flow-limiting obstructive CAD, while the rest will be considered to have non-flow limiting obstructive CAD (if also $>50\%$ stenosis on ICA). If stenosis severity turns out to be $< 50\%$ after ICA (the gold standard), we will conclude that these patients have non-obstructive CAD. (Figure 1). Patients with 30% to 49% obstructive disease, according to CCTA, will be referred to optimal follow up care only. Any in this group who have positive CT-FFR will return for

ICA with invasive FFR measurement, and follow the protocol for those with 50% to 100% obstruction.

Figure 1:

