14.1 Sample Size Determination

Based on data from Stony Brook and confidential data HeartFlow reported from providers who have been using CT-FFR in a similar manner as we propose for this study, we estimated that about 60% of stable chest pain patients who had CCTA were diagnosed with coronary stenosis of 30% to 90% and received CT-FFR. Of these patients, about 35% had an ICA test, and 14% of those had a negative ICA test result (i.e. the false-positive rate of CCTA+CT-FFR was 14%). A sample of 121 patients who received ICA will yield 80% statistical power of detecting a 60% reduction in the false-positive rate (from 14% to 6%), based on a two-sided one sample Chi-square test with 0.05 significance level. Assuming a similar prevalence of flow-limiting obstructive CAD and assuming that similar proportions of stable chest pain patients who had CCTA will receive CCT-FFR and then ICA, 576 stable chest pain patients who had CCTA need to be complete the clinical trial. In order to target 576 subjects completing the trial, we estimate that number of patients, it will be necessary to 594, because 18 patients who enrolled were screen failures.

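### The planned sample size is given as an unlabelled 572 in three sections, which matches neither the 576 completers nor the 594 enrolled derived in Section 14.1

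*Combined protocol and SAP*

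**What the plan says.** Three places give 572:

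- Study Summary: "Number of subjects projected for the entire study 572".
- Section 5 (Resources), in a feasibility paragraph on scan volume: "our target of 572 cases should be achievable".
- Section 6.1 (General Design): "572 consecutive patients who present to Lenox Hill Hospital Outpatient Clinics for CCTA", with the sentence going on to tie these patients to the inclusion criteria.

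Section 14.1 (Sample Size Determination) gives different numbers and is the only section that derives any:

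- "A sample of 121 patients who received ICA will yield 80% statistical power", for a fall in the false-positive rate from 14% to 6%, "based on a two-sided one sample Chi-square test with 0.05 significance level".
- About 60% of patients having coronary CT angiography (CCTA) go on to CT-FFR, and about 35% of those have ICA.
- "576 stable chest pain patients who had CCTA need to be complete the clinical trial".
- For enrolment, "it will be necessary to 594, because 18 patients who enrolled were screen failures".

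All four are current text. No section derives 572, labels it, or links it to 576 or 594.

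**The concern.** A planned sample size should be one number with one meaning, or a labelled pair for enrolled and evaluable patients. Here the sections that describe the study give one figure, and the section that justifies the size gives two others. No reading of 572 removes the conflict: as completers it disagrees with 576, and as enrolment it disagrees with 594.

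What is at stake is mainly whether the target can be interpreted. A trial that enrolled 572 could be reported as having met its target under the Summary and as under-recruited under Section 14.1. A reader also cannot tell which count the 80% power statement belongs to. Whether power itself suffers depends on what 572 counts, so that needs to be worked out for each reading.

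**Working it through.** **Inputs, all from Section 14.1 except 572.** Null rate p0 = 0.14; alternative p1 = 0.06; two-sided alpha 0.05; power 80%; one-sample chi-square test; share receiving CT-FFR 0.60; share of those having ICA 0.35; 18 screen failures. The figure 572 comes from the Study Summary, Section 5 and Section 6.1.

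**Step 1: reproduce the ICA count.** One-sample proportion, normal approximation, no continuity correction:

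n = [z(0.975)·√(p0(1−p0)) + z(0.80)·√(p1(1−p1))]² / (p0−p1)²

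= [1.960·√0.1204 + 0.842·√0.0564]² / 0.08² = 120.99, rounded up to 121.

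This matches the plan. It rests on the stated 6%. The accompanying description as a 60% reduction is loose (1 − 0.06/0.14 = 57.1%), but it is not the input that yields 121.

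**Step 2: reproduce completers and enrolment.** ICA yield per CCTA patient = 0.60 × 0.35 = 0.21. Completers = 121 / 0.21 = 576.2, given as 576. Enrolled = 576 + 18 = 594. Both match.

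**Step 3: see where 572 sits.** 120 / 0.21 = 571.4, which rounds up to 572. So 572 is what the same method gives for 120 ICAs, one fewer than 121. That it arose this way is an inference; the document does not say so.

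**Step 4: power under each reading.** The formula that reproduces Section 14.1 is

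power = Φ{ [0.08·√n − 1.960·√0.1204] / √0.0564 }

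| Reading | Evaluable | Expected ICAs (× 0.21) | Power |
|---|---|---|---|
| Section 14.1 | 576 | 120.96 | 80.0% |
| 572 means completers | 572 | 120.12 | 79.6% |
| 572 means enrolled, 18 lost | 554 | 116.34 | 77.9% |

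Shortfall: 576 − 572 = 4 completers, or 594 − 572 = 22 enrolled.

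**Step 5: check that the small differences are not over-read.** Exact binomial power of the uncorrected chi-square test is not monotone in n: 73.9% at 116 ICAs, 83.5% at 117, 81.6% at 120 and 80.9% at 121. A difference of one ICA therefore carries no meaning. The ICA count is also random. Treating it as binomial with a 21% yield and averaging exact power over it gives:

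| Evaluable | Averaged exact power | Chance of at least 121 ICAs |
|---|---|---|
| 576 | 80.2% | 51% |
| 572 | 79.9% | 48% |
| 554 | 78.4% | 33% |

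The averaged figures agree with Step 4: almost nothing is lost if 572 means completers, and about 2 points if it means enrolment before screen failures.

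**The case against.** The strongest reply is that this is a labelling matter with little statistical content. Section 14.1 has no arithmetic error, and it gives an explicit derivation and enrolment number for anyone who reads it. Section 6.1 ties 572 to patients who meet the inclusion criteria, which fits a count taken after screen failures. On that reading the like-for-like gap is 4 in 576, or 0.7%, and subtracting the 18 from 572 would remove screen failures twice. The yields behind 576 are themselves given only as approximate. The Section 5 feasibility argument, which rests on more than 1,000 scans a year, is hardly affected by 572 versus 594. Finally, the 80% belongs to a one-sample test, whereas Sections 6.1 and 6.2 plan a comparison with a retrospective control group, so refining it by a point or two says little about that comparison.

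Most of this stands, and it limits the size of the point. A reader might infer that the site is told to stop at 572 enrolled, and that recruiting to 572 forfeits the stated 80% power. The documents support neither. All three passages give a projection or target, not a stopping instruction; none calls 572 an enrolment count; and 572 evaluable patients keep 80% in effect.

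The reply does not remove the contradiction. The Summary's wording about the entire study can equally be read as total enrolment, nothing settles the choice, and even the favourable reading leaves 572 different from 576.

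**Conclusion.** The inconsistency is real: 572 appears unlabelled in three sections and equals neither the 576 completers nor the 594 enrolled of Section 14.1. It is a disagreement between sections; Section 14.1 reproduces in full from its own inputs.

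The size is small. The loss is 0.4 points of power if 572 means completers, and about 2 points if it means enrolment before 18 screen failures. The 22-patient shortfall and the power of about 78% are the worst-case reading, not an established fact. These figures assume Section 14.1's rates (14% and 6%), its 21% ICA yield and its one-sample test; they do not describe power for the comparison with the retrospective controls. Severity is minor.

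**What to change.** Replace 572 in the Study Summary, Section 5 and Section 6.1 with the pair from Section 14.1, labelled: 576 completing, 594 enrolled.

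If 572 is the intended target, derive it in Section 14.1, say there and in the other three places what it counts, and restate the consequences: about 120 ICAs and 79.6% power if it means completers; about 116 ICAs and about 78% if it means enrolled.

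The first option costs a change of wording in three places, with no change to the design or the calculation. The second also needs Section 14.1 rewritten, with a slightly lower stated power.

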6.1 General Design

This will be a prospective clinical trial designed to evaluate the incremental benefit of virtual FFR measured from CCTA, compared to invasive FFR and CCTA for the detection of flow-limiting coronary stenosis, as defined by invasive FFR ≤ 0.8 and vessel diameter of $\geq 2\text{mm}$.

572 consecutive patients who present to Lenox Hill Hospital Outpatient Clinics for CCTA due to chest pain or stable angina over a ten month period and meeting the study inclusion criteria are eligible for the study (Figure 1). Our team will employ CCTA-appropriateness criteria to ensure proper selection of patients, derived from the Appropriate Use Criteria for Cardiac Computed Tomography published in 2010 and jointly authored by multiple societies including ACCF, SCCT, and ACR [10]. FFR-CT measurements will be performed by a core laboratory in a blinded fashion. All eligible patients will undergo 64-slice or greater multi detector CCTA and CT-FFR measurements. The severity of the stenosis will be determined on site by level III CCTA readers. Patients with obstructive lesions of (30% to 100% stenosis) will receive Stress-MPI, per SOC protocol, and CT-FFR. Patients with positive Stress-MPI and CCTA (50% - 70%) or positive CCTA (71% to 100%) will undergo ICA with invasive FFR measurement in accordance to accepted guidelines and established practice standard. Those patients with invasively measured FFR ≤ 0.8 and with vessel diameter of $\geq 2\text{mm}$, or those who require revascularizations based on invasively estimated stenosis severity will be considered to have flow-limiting obstructive CAD, while the rest will be considered to have non-flow limiting obstructive CAD (if also $>50\%$ stenosis on ICA). If stenosis severity turns out to be $< 50\%$ after ICA (the gold standard), we will conclude that these patients have non-obstructive CAD. (Figure 1). Patients with 30% to 49% obstructive disease, according to CCTA, will be referred to optimal follow up care only. Any in this group who have positive CT-FFR will return for

ICA with invasive FFR measurement, and follow the protocol for those with 50% to 100% obstruction.

Figure 1:

In order to assess the primary endpoint of comparison of event rates for patients treated with CCTA and FFR-CT, we will perform a retrospective chart review of Invasive Coronary Angiograms performed at Lenox Hill Hospital from 2014 to 2018. We will specifically review Cardiac Catheterization reports to screen patients and record data for cases where the indication for Catheterization was (1) Positive stress test and/or (2) Positive CCTA. Based on the catheterization report we will determine whether the patient had obstructive coronary artery disease with/without flow limitation, in the same manner and following the same definitions as those used to categorize level of obstruction in subjects enrolled in the prospective cohort of the study. This data will be used as comparison/control group to assess trends and rates of invasive coronary catheterization when no intervention is necessary, in cases where CCTA and/or stress test without CT-FFR was used to determine the need for cardiac catheterization. Only the minimum amount of data required for a robust comparison of event rates will be collected.

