8.3 Method for Assigning Subjects to Treatment Groups

This is not a randomized study. Treatment assignments will follow the clinical protocol.

Once the CCTA results are interpreted by the physician, the physician will order CT-FFR exams for patients whose level of stenosis by CCTA standards is 30% to 100%.

If CT-FFR is positive patients will be referred for Cardiac Catheterization and invasive FFR.

If CT-FFR is negative, and level of obstruction is 30 to 49% by CCTA standards, patients will be referred to optimal medical care.

If CT-FFR is negative and level of obstruction is 50% to 70% by CCTA standards, patient will be referred for stress MPI. If stress MPI is positive patients will be referred for Cardiac Cath and invasive FFR. If stress MPI is negative, patients will be referred to optimal medical care.

If the patient has had a stress MPI within one year of the CCTA exam and the CCTA exam result is 50% to 70% obstructive, the physician will rely on the prior stress testing result, rather than repeating the stress test. If the stress testing results was negative, the patient will be referred to optimal medical care. If, in the investigator's opinion, the results indicate that the patient is at increased risk of obstructive disease, when considered with the CCTA findings, the patient will be referred to Cardiac Cath and Invasive FFR.

If CT-FFR is negative and level of obstruction is 70% to 100% by CCTA standard, patient will be referred to Cardiac Cath and Invasive FFR.

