*Patients who have borderline obstructive disease (50% to 70% stenosis) who have negative CT-FFR will be referred for Stress MPI to confirm, unless the patient has had stress testing within a year of the CCTA. This is an accepted practice as part of the standard of care at Lenox Hill Hospital. If the stress test is negative, the patient will be referred to his/her physician for follow-up. If the stress test is positive, the patient will be referred to Invasive Coronary Angiography for Invasive FFR and diagnostic cardiac catheterization. If the patient has had a history of negative stress testing within a year of the CCTA, then the patient will be referred to his/her physician for follow-up. If the patient's prior stress test had findings that, in the investigator's opinion, increase the patient's risk of obstructive disease when viewed with the CCTA findings, the patient will be referred to Invasive Coronary Angiography for diagnostic cardiac catheterization and Invasive FFR. This is an accepted practice as part of the standard of care at Lenox Hill Hospital.**

Patients who have borderline obstructive disease (50% to 70% stenosis) who have positive FFR will be referred for Invasive Coronary Angiography for Invasive FFR and diagnostic

*cardiac catheterization. This is an accepted practice as part of the standard of care at Lenox Hill Hospital. **

Patients with 71% or greater stenosis will be referred for Invasive Coronary Angiography for Invasive FFR and diagnostic cardiac catheterization. This is an accepted practice as part of the standard of care at Lenox Hill Hospital.

**In current standard of care practice at Lenox Hill Hospital, for borderline obstructive coronary disease, the decisions as to whether to proceed with stress testing or refer to invasive coronary angiography is left to the medical discretion of the attending cardiologist.*

Invasive Coronary Angiography and Invasive FFR are considered to be the gold standard procedures for evaluation of obstructive coronary artery disease. Patients deemed to be at high risk for obstructive disease based on CCTA or Stress testing are referred for invasive testing to determine whether cardiac intervention consisting of Percutaneous Coronary Intervention or Coronary Artery Bypass Graft is necessary.

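### At 50–70% stenosis the sections disagree on who goes to invasive angiography, most sharply for CT-FFR-positive patients with a negative stress MPI in the past year

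*Combined protocol and SAP*

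**What the plan says.** Section 6.1 (General Design) states that patients with 30–100% stenosis "will receive Stress-MPI, per SOC protocol, and CT-FFR". It then gives the referral rule: "Patients with positive Stress-MPI and CCTA (50% - 70%) or positive CCTA (71% to 100%) will undergo ICA with invasive FFR measurement". In 6.1, CT-FFR triggers ICA only in the 30–49% group, where a positive result brings the patient back for ICA with invasive FFR.

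The other sections give CT-FFR a wider role:

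- Section 2: "If the noninvasive FFR diagnosis indicates obstructive disease, the patient will undergo cardiac catheterization with invasive FFR".
- Section 8.3: "If CT-FFR is positive patients will be referred for Cardiac Catheterization and invasive FFR", with no MPI condition. MPI is for the CT-FFR-negative: "If CT-FFR is negative and level of obstruction is 50% to 70% by CCTA standards, patient will be referred for stress MPI". For the top band: "If CT-FFR is negative and level of obstruction is 70% to 100% by CCTA standard, patient will be referred to Cardiac Cath".
- Section 9, on this exact stratum: "Patients who have borderline obstructive disease (50% to 70% stenosis) who have positive FFR will be referred for Invasive Coronary Angiography".
- Section 9.2 makes catheterization the second visit for any positive CT-FFR.

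Three sections also have a rule for a stress test done within the past year. In 8.3, at 50–70%, "the physician will rely on the prior stress testing result, rather than repeating the stress test", and a negative prior result leads to medical care. That paragraph does not restate the CT-FFR result. In 9.2 the matching lines restate neither the CT-FFR result nor the stenosis band. Section 9 places the rule inside its paragraph on CT-FFR-negative patients at 50–70%.

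**The concern.** A site following 6.1 finds no CT-FFR route to ICA at 50–70%. A site following section 9 catheterizes every CT-FFR-positive patient in that band. A site following 8.3 or 9.2 can find two answers for one patient.

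Three things depend on the answer:

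- **The procedure itself.** The rule decides whether the patient is catheterized.
- **The primary endpoint.** Section 6.2 counts an event when ICA is done and no intervention turns out to be needed. A patient not sent to ICA cannot have the event.
- **Diagnostic accuracy (Aim 1).** Section 14.2 calls the CCTA+CT-FFR strategy positive when ICA is required. The routing therefore sets the index-test result and also who receives the reference standard.

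**Working it through.** **Step 1: the routes side by side.** The entries are what each text prescribes.

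| CCTA stenosis and CT-FFR | 6.1 | 8.3 | 9 | 9.2 |
|---|---|---|---|---|
| 30–49%, positive | ICA | ICA | not stated separately | ICA |
| 50–70%, positive, no recent stress test | ICA stated only for positive MPI | ICA, no MPI ordered | ICA, no MPI ordered | ICA, no MPI ordered |
| 50–70%, positive, negative stress test in past year | no route to ICA stated | ICA by the CT-FFR rule; medical care by the prior-stress rule | ICA | ICA by the CT-FFR rule; follow-up care by the prior-stress line |
| 50–70%, negative, no recent stress test | MPI; ICA if positive | same | same | same (with Visit 3) |
| Exactly 70%, negative | MPI band | both MPI and ICA | MPI band | both MPI and ICA |
| 71–100% | ICA | ICA | ICA | ICA |

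Section 2 sends positive CT-FFR to catheterization without naming a band.

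**Step 2: where the conflict lies.** No section contradicts another on ICA for CT-FFR-positive patients at 30–49%, or for patients at 71–100%. The disagreement is at 50–70% with positive CT-FFR, plus a boundary overlap at exactly 70%.

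Under 8.3, 9 and 9.2 a CT-FFR-positive patient is not ordered a new MPI. Within those sections, positive CT-FFR with negative MPI can therefore arise only through a recent prior test. That is the row in which 8.3 and 9.2 each give two instructions. Section 9 does not, because its prior-test rule sits under the CT-FFR-negative condition.

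**Step 3: the plan's own numbers.** Section 14.1 uses a two-sided one-sample chi-square test, 14% against 6%, alpha 0.05 and 80% power:

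n = [(1.960 × √(0.14 × 0.86) + 0.842 × √(0.06 × 0.94)) / 0.08]² = 120.99, rounded up to 121 with ICA.

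121 / (0.60 × 0.35) = 576.2, against 576 stated. Both figures reproduce, and nothing here challenges them. They imply 576 × 0.60 ≈ 346 patients with CT-FFR.

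**Step 4: can the affected number be found?** It would need the share of the 346 at 50–70%, the CT-FFR-positive rate there, and the MPI-negative rate among those. For the contradiction inside 8.3 and 9.2 it would also need the share with a stress test in the past year. The documents give none of these.

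Purely as an assumption, take 20–40%, 30–50% and 30–70% for the first three, with an MPI result for everyone:

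- low: 346 × 0.20 × 0.30 × 0.30 ≈ 6
- high: 346 × 0.40 × 0.50 × 0.70 ≈ 48

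The width of that range shows only that the size is unknown. The group with a recent prior test would be some unknown fraction of it.

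**The case against.** **Section 6.1 is a summary and conflicts partly by omission.** It does not say that positive MPI is the only route, and section 9 states the 50–70% rule outright. Denying ICA to a CT-FFR-positive patient at 50–70% while granting it at 30–49% would be clinically odd, so the intended rule is probably section 9's. This stands, and it lowers the severity. It does not remove the need to correct 6.1, which names a CT-FFR route for one band and leaves it out for the next.

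**The standard-of-care qualifier in 6.1 leaves room.** Section 9 notes that for borderline disease the choice between stress testing and ICA rests with the attending cardiologist. So 6.1 need not mean MPI for every patient. The qualifier still gives CT-FFR no referral role at 50–70%.

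**The prior-stress lines can be read in context.** In 8.3 and 9.2 they follow a sentence about CT-FFR-negative patients and may have been meant to inherit that condition. This is plausible. But 8.3 restates the stenosis band and not the CT-FFR result, so a literal reader gets two answers.

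**Figure 1 may settle the matter.** It is not reproduced in the text available here, which is no fault of the plan. A clear figure would still leave the text to be aligned with it.

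**A reader might infer that a few misrouted patients would overturn the result.** Under 14.1's test, 7 negative ICAs of 121 give p = 0.009, and three more negatives (10 of 124) give p = 0.057. The documents do not support the inference, for three reasons:

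- It assumes that no positive ICAs come with the three negatives. With two, 10 of 126 gives p = 0.0498.
- The direction is unknown. Section 14.1 draws its rates from providers using CT-FFR in a similar way, so the 121 may already include CT-FFR-triggered ICAs. Removing three negatives gives 4 of 118, p = 0.0009.
- Section 6.2 names t-tests and a hazard model for the primary comparison, not this one-sample test.

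**A reader might also infer that the primary comparison must be reinterpreted by what triggered each ICA.** That is a separate question about the historical control. It does not follow from this inconsistency.

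**Conclusion.** The point holds as an internal inconsistency that is wrong as written, of minor to moderate severity. Section 6.1 departs from 2, 8.3, 9 and 9.2 on the role of CT-FFR at 50–70%. Sections 8.3 and 9.2 each contain opposite instructions for a CT-FFR-positive patient at 50–70% with a negative stress MPI in the past year. A lesser overlap exists at exactly 70% for CT-FFR-negative patients.

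It matters because of what the rule controls. No effect on the trial's result has been shown, the number affected cannot be derived, and no claim about significance should be attached. The conclusion rests on the text alone and assumes that Figure 1 does not override it.

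**What to change.** Let section 9 govern, and make these changes:

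1. Rewrite 6.1 so that positive CT-FFR at 30–100% goes to ICA, stress MPI is only for CT-FFR-negative patients at 50–70% without a stress MPI in the past year, and 71–100% goes to ICA.
2. In 8.3 and 9.2, add the condition that CT-FFR is negative to the prior-stress lines.
3. Use one cut-point throughout. At present 6.1 and 9 start the top band at 71%, while 8.3 and 9.2 start it at 70%.
4. Confirm that Figure 1 shows the same routing, since 14.2 refers to it for the index-test definition.

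Optionally, add one case report form field for what triggered each ICA (CCTA stenosis, CT-FFR, new MPI or prior MPI). It can be filled from charts, including for patients already enrolled.

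The cost is a few lines of text and a check of one figure. The sample size does not change.
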